### **9.3.4 HbA1c**

The absolute change in HbA1c (%) from baseline up to the common study end date.

### **9.3.5 EQ-5D Patient Questionnaire**

EQ-5D is a standardized measure of health status developed by the EuroQol Group in order to provide a simple, generic measure of health for clinical and economic appraisal. The EQ-5D as a measure of health-related quality of life, defines health in terms of 5 dimensions: mobility, self-care, usual activities, pain/discomfort, anxiety/depression. Each dimension can take one of three responses (3 ordinal levels of severity): 'no problem' (1). "some problems" (2). "severe problems" (3). Overall health state is defined as a 5-digit number. Health states defined by the 5-dimensional classification can be converted into corresponding index scores that quantify health status, where

0 represents 'death' and 1 represents “perfect health” (See [Appendix G](#)). If response to one or more dimension is missing, the index score will be missing.)

EQ-5D variables include response of each EQ-5D items, index score and change of index score from baseline Week (39).

This questionnaire will only be administered in patients receiving the double-blind treatment. Patients who will prematurely discontinue will be asked to fill in this questionnaire until the early end of treatment visit (V70) to be performed at the time of discontinuation.

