- g Hematology includes: complete blood cell count (CBC) including hematocrit, hemoglobin, red blood cell count, reticulocyte count, white blood cell count with differential count, and platelets (Note: reticulocyte not done at V1). Chemistry includes: glucose, sodium, potassium, chloride, bicarbonate, calcium, phosphorous, urea nitrogen, creatinine, uric acid, LDH, total protein, albumin, and  $\gamma$ GT.
- h Liver panel: ALT, AST, alkaline phosphatase (ALP), and total bilirubin. Hepatitis C antibody: In case of positive hepatitis C antibody test, a blood sample will be collected at a subsequent visit and sent to Covance Central Lab for further confirmatory testing
- i Pregnancy tests (serum, urine) in Women of Child Bearing Potential (WOCBP) only. Urinalysis to be performed only at selected sites (see [Section 10](#)).
- j Library samples should be collected, as permitted by local regulatory policies. They may be stored for up to 10 years or as permitted by local regulatory policies, whichever is shorter, for exploratory research of PCSK9 levels, PCSK9 function, effect(s) of PCSK9 inhibition with a monoclonal antibody, lipoprotein sub-fraction, inflammation, and cardiovascular risk markers (eg, lipoprotein-associated phospholipase A2).
- k If blood sample not collected at randomization, could be collected at any time during the study.
- l EQ-5D patient questionnaire will only be administered in patients still on treatment, for prematurely (permanently) discontinued patients the last administration will be done at the early end of treatment visit.
- m Common study end date (CSED) will occur 24 months after the closing of randomization ex-China or after the target number of events (1613) is reached whichever comes last. A final clinic visit V30 (CSED visit, Month 64) should be completed within 30 days of CSED for all randomized patients regardless of the compliance with study treatment (see [Section 10.1.5.1.4](#)). Reduced assessments in 'Prematurely discontinued patients' column apply only if V30 occurs more than 6 months after V70 (see [Section 10.3.4](#)).

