3.4.7.4 Analyses of lipid parameters

The lipids variables (see Section 3.1.5.1) will be analyzed using an ITT approach (based on the ITT population) including all lipid values, regardless of whether the patient was continuing therapy or not. In addition, analyses will also be conducted using an on-treatment approach (based on the randomized and treated population) only including lipid data collected during the treatment period.

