3.4.7.4.1 ITT analyses

A pattern-mixture model approach (see Appendix F) will be used with a different imputation strategy applied for missing lipid values during the treatment period (ie, within the time period from the first double-blind IMP injection up to the day of the last double-blind injection +21 days) and missing lipid values after treatment discontinuation (ie, after the day of last injection +21 days) based on the following assumptions:

- Patients within 21 days of their last double-blind IMP injection would continue to show benefit from treatment similar to that observed at the scheduled time point. Therefore, lipid values missing during the treatment period (samples obtained outside the specified window, no blood sample available although visit was performed, etc) should be considered "Missing At Random" and imputed based on other on-treatment measurements;
- Patients who stopped taking their study treatment no longer benefited from it after discontinuation and thus tended to have lipid values returning to baseline. Thus lipid values missing after treatment discontinuation will be imputed based on patient's own baseline value.

Missing lipid values will be imputed 10 times using the MI SAS® procedure, to generate 10 complete data sets. The percent change from baseline and/or the absolute change from baseline at a pre-specified time point will be derived from observed and imputed lipid value at this time point. Imputed values for time points after CSED will be discarded.

TGs and Lp (a) data will be log-transformed before imputation process and then back-transformed to create the imputed data sets.

The completed data sets will be analyzed using an analysis of covariance (ANCOVA) model for continuous lipid variables other than Lp (a) and TGs or a robust regression (6) model for Lp (a) and TGs continuous variables with treatment group as fixed effect, and the baseline lipid value as continuous covariate. The MIANALYZE procedure will be used to generate valid statistical inferences by combining results from the 10 analyses using Rubin's formula.

The number of imputations (10) will be informally verified by replicating sets of 10 imputations and checking whether the combined results are stable. If not stable, the number of imputations will be increased and informally checked as above, and thus until stable estimates are obtained.

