3.4.7.4.2 On-treatment analyses

Analysis of lipid variables will be conducted during the treatment period. Post-treatment data will not be considered.

The lipid variables other than Lp (a) and TGs will be analyzed in the randomized and treated population using a mixed-effect model with repeated measures (MMRM) approach. All post-baseline on-treatment data available within Month 1 to Month 64 analysis windows will be used and missing data will be accounted for by the MMRM model.

The model will include the fixed categorical effects of treatment group (placebo, alirocumab), planned time point (Month 1 to Month 64), treatment-by-time point interaction, as well as, the continuous fixed covariate of baseline lipid value and baseline lipid value-by-time point interaction. This model will be run using SAS Mixed procedure with an unstructured correlation matrix to model the within-patient errors. Parameters will be estimated using restricted maximum likelihood method with the Newton-Raphson algorithm. Denominator degrees of freedom will be estimated using Satterthwaite's approximation. This model will provide baseline adjusted least-squares means estimates over time for both treatment groups with their corresponding SEs and 95% CI. To compare the alirocumab group to the placebo group, appropriate contrasts statement will be used to test the differences of these estimates, at the 2-sided 0.05 level, for the different time points.

Note: in case of computation issue for this approach, multiple imputation under missing-at-random (MAR) assumption will be conducted, followed by an ANCOVA model.

The Lp (a) and TGs will be analyzed in the randomized and treated population using multiple imputation (same imputations as in Section 3.4.7.4.1 without discarding imputations of missing values during the post-treatment period (see Appendix F).

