3.4.7.6 Analyses of quality of life/health economics variables

The analysis of data from EQ-5D instrument will be performed on the ITT population.

Baseline is defined as the Visit 3 (Day 1) evaluation. Analysis window will be used to assign the measurements to time points (see Section 3.5.4).

Individual EQ-5D items

Response for each one of the 5 EQ-5D items will be summarized by time point for each treatment group with number (%) of patients reporting level 1 (no problems), level 2 (some problems), and level 3 (extreme problems) by item.

EQ-5D utility score

The raw value and the change from baseline of the utility score will be summarized using mean, median, Q1, Q3, SD, minimum, and maximum for each post-baseline visit. Cumulative distribution functions for the change in utility score from baseline will be displayed by treatment groups over time.

The change from baseline in utility score over time will be analyzed using a MMRM model with fixed categorical effects of treatment group, planned time points up to the CSED, treatment-by-time point interaction, as well as, the continuous fixed covariates of baseline value and baseline value-by-time point interaction.

Note: In case of computation issue for this approach, multiple imputation under MAR assumption will be conducted, followed by an ANCOVA model.

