3.5.4 Windows for time points

Data analyzed by time point (including lipid data, laboratory safety data, vital signs, ECG, ADA, EQ-5D) will be summarized using the time windows given in Table 8 below. These time windows will be applicable for all analyses, and they are defined to provide more homogeneous data for time point-specific analyses.

Statistical Analysis Plan SAR236553/REGN727-EFC11570 - alirocumab 11-Oct-2017 Version number: 3

Time point	Targeted study days	Time windows
Month 1	30	16 to 44
Month 2	60	45 to 75
Month 4	122	107 to 137
Month 8	244	229 to 259
Month 12 to Month 24	Number of months of the planned visit x 30.4375 and rounded to the nearest entire number of days	Targeted study day ±21 days
Beyond Month 24	Number of months of the planned visit x 30.4375 and rounded to the nearest entire number of days	Targeted study day ±28 days

Table 8 - Time windows definitions

If multiple valid values of a variable exist within a time window, the nearest from the targeted study day will be selected for the statistical analysis by time point. If the difference is a tie, the value after the targeted study day will be used. If multiple valid values of a variable exist within a same day, then the first value of the day will be selected.

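### EQ-5D stops at V70 in patients who stay in follow-up, so the MMRM to the CSED comes close to a stay-on-treatment effect, which the SAP does not state

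*Protocol*

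**What the plan says.** **Collection.** Protocol 9.3.5 states: "This questionnaire will only be administered in patients receiving the double-blind treatment". It ends the questionnaire at V70 for patients who discontinue. Footnote l, attached to the EQ-5D row of the flow chart in Protocol 1.2.1, repeats this: "EQ-5D patient questionnaire will only be administered in patients still on treatment". The V30 list for prematurely discontinued patients (Protocol 10.1.5.4.2) does not contain EQ-5D. The same patients must remain in the study to the CSED (footnote n; 10.1.5.3; 10.3.4).

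Other protocol text points the other way:
- Footnote n, 10.1.5.3 and 10.3.4 ask for the usual assessments, IMP procedures aside, for 6 months after V70 and do not except EQ-5D.
- Footnote m applies the reduced V30 list only when V30 is more than 6 months after V70. Otherwise the completers' list, which includes EQ-5D (10.1.5.4.1), would seem to apply.
- The flow-chart row marks EQ-5D at V30 for discontinued patients.

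**Analysis.** SAP 3.4.7.6: "The analysis of data from EQ-5D instrument will be performed on the ITT population". The utility model is an MMRM with "fixed categorical effects of treatment group, planned time points up to the CSED", with MAR imputation followed by ANCOVA as the fallback. No sensitivity analysis is planned. Values are allocated to time points through Table 8 (SAP 3.5.4): "Data analyzed by time point (including lipid data, laboratory safety data, vital signs, ECG, ADA, EQ-5D) will be summarized using the time windows".

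**The concern.** EQ-5D is not lost here because patients leave. The protocol stops asking patients whom it keeps seeing. An MMRM, or imputation under MAR, then fills the period after discontinuation with what similar patients still on drug reported. The question actually answered is roughly what the utility difference would have been had nobody stopped. A reader who sees an all-randomized analysis running to the CSED may take it as the difference regardless of stopping.

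For lipids the SAP draws this distinction itself. Its ITT analysis uses values "regardless of whether the patient was continuing therapy or not" and does not assume MAR after a stop, on the ground that "Patients who stopped taking their study treatment no longer benefited from it after discontinuation" (3.4.7.4, 3.4.7.4.1). A near-identical MMRM is kept separate as on-treatment: "Analysis of lipid variables will be conducted during the treatment period. Post-treatment data will not be considered" (3.4.7.4.2). EQ-5D has neither the off-treatment data nor the non-MAR handling. What is at stake is the interpretation of one exploratory endpoint that Protocol 9.3.5 describes as serving clinical and economic appraisal.

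**Working it through.** The documents state no sample size, SD, effect or discontinuation rate for EQ-5D, so there is no figure to reproduce.

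**1. Assessments lost by rule.** Planned post-baseline EQ-5D: M2, 4, 8, 12, 16, 20, 24, 30, 36, 42, 48, 54 and 60 if before the CSED, plus V30. Entry is at mid-month m = 1 to 40 and follow-up is 64 − (m − 0.5) months. Weights are the monthly rates in Protocol Table 3 (they sum to 18,244 and are used as weights only).
- Mean follow-up 40.4 months; mean planned 10.25.
- Permanent stop just after M12: mean lost 6.25 of 10.25.
- Range: 4 of 8 at about 24 months of follow-up, to 10 of 14 for entry months 1 to 4 (3 × 32 + 64 = 160 patients).
- Patients from China followed for less than 24 months are not covered.

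**2. How much V70 can contribute.** Days inside a Table 8 window for an EQ-5D time point:
- To day 731: 3 × 31 + 3 × 43 + 22 = 244; 244/731 = 33%.
- To day 1948 (M64): 93 + 4 × 43 + 6 × 57 + 29 = 636; 636/1948 = 33%.

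If V70 dates are spread evenly, about one V70 value in three can enter the by-time-point analysis, and fewer where a scheduled value lies nearer the target day.

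**3. How much V30 would contribute if collected.** V30 follows a calendar date, not a study month. With Table 3 weights, entry spread within each month and V30 spread over CSED to CSED + 30 days, about 30% of V30 values fall inside any EQ-5D window and well under 1% inside the M64 window. About 70% would be dropped. Lipids avoid this because SAP 3.4.7.4.1 takes the value at the CSED visit; 3.4.7.6 has no such rule.

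**4. What the MMRM estimates.** Let d be the share off drug at the CSED and k the share of the effect kept after stopping. The stay-on effect divided by the effect regardless of stopping is 1/[(1 − d) + dk]. With k = 0 this is 1/0.90 = 1.11 at d = 10%, 1/0.80 = 1.25 at 20% and 1/0.70 = 1.43 at 30%. With k = 1 it is 1.

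Simulation of an unstructured MMRM with no data after V70. Assumed, not in the documents: stay-on effect 0.02, SD 0.2, correlation 0.6, 7 visits, stopping dependent on the last observed score. The 9,300 per arm is the planned size.

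| d | k | MMRM | if all stayed on | regardless of stopping |
|---|---|---|---|---|
| 0.10 | 0 | 0.0197 | 0.0199 | 0.0180 |
| 0.20 | 0 | 0.0198 | 0.0203 | 0.0164 |
| 0.30 | 0 | 0.0211 | 0.0209 | 0.0152 |
| 0.20 | 0.5 | 0.0200 | 0.0203 | 0.0184 |
| 0.20 | 1 | 0.0204 | 0.0205 | 0.0205 |

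The MMRM tracks the stay-on effect. With final-visit scores observed and entering the model (d = 0.20, k = 0), it gives 0.0153 against 0.0153 regardless of stopping. That run treats the final visit as a common time point, so it carries over only with a CSED-value rule.

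**5. Range for the gap.** Gap = dA × sA − dP × sP, where s is true minus MAR-predicted utility after stopping (all values assumed):
- equal d and equal s: 0;
- s of −0.06 v −0.05: 0.10 × (−0.01) = −0.001 at d = 10%, 0.25 × (−0.01) = −0.0025 at d = 25%; the sign reverses if the arms do;
- s = −0.10 in one arm only: 0.10 × 0.10 = 0.010 to 0.25 × 0.10 = 0.025 in size.

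The largest simulated gap is 0.0209 − 0.0152 = 0.0057, at d = 30% with the effect wholly lost.

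**The case against.** Five points can be made for the plan.

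- **The population name is correct.** SAP 3.3.1.1 defines ITT as all randomized patients analysed as allocated, and 3.4.7.6 says no more than that. This stands. A reader might infer that the analysis is mislabelled; the text does not support that. What is missing is a statement of the estimand.
- **It is not an on-treatment analysis.** In the SAP that term means data up to the last double-blind injection + 21 days (3.1.4, 3.4.7.4.2). EQ-5D has no such cut-off. Visits during interruptions treated as temporary, visits after the blinded switch to placebo and some V70 values are off drug and still enter. This stands, so the estimate is only close to the stay-on effect.
- **The specific rule outranks the general one.** Footnote l sits on the EQ-5D row, 9.3.5 agrees, and the reduced V30 list omits the form. The V30 mark is weak evidence, because vital signs are marked in the same column and are also absent from that list. This mostly stands. Footnote m and the 6-month text still allow sites to differ, so one cannot say that no EQ-5D is ever obtained after V70.
- **Collecting V30 alone would achieve little.** This stands (step 3) and shapes the fix.
- **It is a deliberate simplification on an exploratory endpoint** (SAP 3.1.5). This stands and limits the weight of the point.

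**Conclusion.** The point holds as a minor one. By the specific protocol rule, utilities after permanent discontinuation are missing by design, and the SAP predicts them under MAR mainly from patients still on drug. The EQ-5D estimate to the CSED therefore lies near the hypothetical effect of staying on treatment, and the SAP does not say so.

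The size cannot be computed from the documents. The simulated gaps and the small between-arm differences give 0 to about 0.006 utility units; 0.010 to 0.025 needs a large post-stop shortfall in one arm only. There is no gap if the effect persists off drug, or if both arms stop equally often and are equally mispredicted. The conclusion assumes that sites followed 9.3.5 and footnote l; if they followed the V30 mark or the 6-month text, some of the missing values exist. A reader might infer that the trial's conclusions are affected. They are not: EQ-5D lies outside the testing hierarchy, and the primary and main secondary endpoints are followed to the CSED regardless of treatment.

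**What to change.** 1. **Protocol.** Reconcile 9.3.5, the EQ-5D flow-chart row, footnotes l, m and n, and sections 10.1.5.3, 10.1.5.4.2 and 10.3.4. Collect EQ-5D in discontinued patients at clinic visits they already attend, at least at V30. First randomization on 02 November 2012 plus 64 months is about March 2018 and SAP version 3 is dated 11-Oct-2017, so V30 is the realistic point.
2. **SAP 3.4.7.6.** Add a CSED-value rule like the one for lipids, so that V30 values are used wherever they fall relative to Table 8.
3. **If the data are not collected,** state that utilities after V70 are missing by design and that the MMRM assumes MAR, which targets a hypothetical estimand. Do not call it on-treatment.
4. **Before unblinding,** add a sensitivity analysis that shifts MAR-imputed post-discontinuation utilities over a range, for example 0 to −0.10, equal and unequal by arm. Imputation from the patient's own baseline should be at most one scenario, because utility need not return to baseline after an event.

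Cost: item 1 needs a short amendment with ethics approval, a five-item form and data entry at visits that were deliberately simplified; patients seen only once a year would still have gaps. Items 2 to 4 need SAP wording and some programming.

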### 9.3.6 Pharmacogenomic Samples

An optional pharmacogenomic sub-study will be conducted to identify genetic associations with clinical or biomarker response to PCSK9 inhibition, hyperlipidemia, or cardiovascular disease. If needed, samples may also be used to identify markers associated with toxicity.

Randomized patients who agree to participate in the genomics sub-study will be required to sign a separate genomics sub-study informed consent form (ICF) prior to collection of the DNA sample. Blood for DNA extraction should be collected before IMP injection (pre-dose) on randomization visit; however, it could be collected at any time during the study. Patients who choose not to enroll in the genomics sub-study are still eligible to enroll in the primary study.

Special procedures for storage and shipping of pharmacogenomic samples are summarized below ([Table 1](#)) and are described in detail in [Appendix B](#).

**Table 1 - Summary of handling procedures for DNA storage samples**

Sample Type(s)	Pharmacogenetics
Blood Sample Volume	6 mL
Tube Type	6 mL Becton Dickinson K2 EDTA VACUTAINER™ Plus tubes with HEMOGARD™ closure (PN367863/4) sterile tubes
Anticoagulant	K2 EDTA
Blood Handling Procedures	Keep blood on ice or frozen at -20°C (or colder) within 30 min of sampling time. DO NOT CENTRIFUGE.
Storage Conditions	In collection tube at approximately -20°C (or colder)

The Sponsor has included safeguards for protecting patient confidentiality. The blood sample and DNA that is extracted from it will be assigned a second number, a Genetic ID (de-identification code) that is different from the Subject ID. This “double coding” is performed to separate a patient’s medical information and DNA data. The clinical study data (coded by Subject ID) will be stored in a distinct database at a different location from the database containing the pharmacogenomic data (coded by Genetic ID). The key linking Subject ID and Genetic ID will be maintained by a third party, under appropriate access control. The matching of clinical data and pharmacogenomic data, for the purpose of data analysis, will be possible only by using this key,

which will be under strict access control. All data will be reported only in coded form in order to maintain confidentiality.

DNA may be stored and used for analyses for up to 15 years from the completion of the Clinical Study Report (CSR). Analyses may include sequence determination or single nucleotide polymorphisms (SNP) from candidate genes. Candidate genes may include (but are not limited to) PCSK9, Apo B and LDL-R. Genome-wide studies, including (but not limited to) SNP analyses and/or genomic sequencing may also be performed.

### **9.3.7 Cardiovascular events of interest (other than efficacy endpoints)**

Clinically significant complications or procedures (not planned at the time of randomization) related to peripheral arterial disease (such as critical limb ischemia, amputation, peripheral revascularization) as well as venous thromboembolic events (deep vein thrombosis, pulmonary embolism) will be collected on the case report form.

## 10 STUDY PROCEDURES

The study consists of a run-in period of at least 2 weeks with randomization no earlier than 4 weeks (28 days) and no later than 52 weeks (+ 5 days) after the index ACS event. The double-blind, placebo-controlled treatment period will continue for 24 months after the closing of randomization ex-China or until the target number of events (1613) is reached whichever comes last (see beginning of [Section 6](#)). The corresponding estimated study duration is approximately 64 months. All randomized patients (whether they are still receiving IMP at the end of the study, or had earlier permanent treatment discontinuation) should have a final visit (CSED visit) between the CSED and CSED + 30 days.

For all visits after Day 1/Month 0 (randomization visit), a timeframe of a certain number of days will be allowed. The window period for visits at Months 1 and 2 are  $\pm 7$  days, and for all other subsequent visits it is  $\pm 14$  days during the double-blind treatment period (NOTE: in case of major IMP issue, please refer to [Section 8.9](#)).

For all visits after Day 1/randomization visit, if one visit date is changed, then the next visit should take place according to the original schedule as outlined [Section 1.2](#).

Ideally all the visits should take place in the morning approximately at the same time. However after randomization in case there is no other possibility for the patient, visits can be arranged later in the day.

For the phone calls/contacts via internet to be performed in between on-site/clinic visits, they should be scheduled with the goal of maintaining a contact with the patient about every 2 months during first 24 months, and about every 3 months thereafter. Having no phone or email contact with a patient for a prolonged period (>4 months) should be avoided as much as possible.

